1.3 Known and Potential Risks and Benefits

ADPKD is a devastating, progressive disease that places a tremendous burden on patients and their families. The risk which a patient is willing to accept is a personal decision based on his/her individual and familial experience with the disease.

The most common observed risks of tolvaptan therapy in adults include those arising from aquaresis (eg, polyuria, pollakiuria, nocturia, thirst, dry mouth), dehydration, electrolyte abnormalities, and gout. While aquaretic events did not contribute to significant subject morbidity over 3 years of study in the pivotal placebo-controlled trial (Trial 156-04-251), they do represent adverse drug reactions which occur early (within days to weeks) and are most likely to limit a subject's ability to continue therapy over a duration of treatment that is likely to provide benefit. While the proposal of increased water ingestion as a mechanism of ameliorating CKD⁹ has not reached medical equipoise, in this trial we believe a general recommendation to do so is reasonable and would recommend ingestion of water adequate to avoid thirst.

The most notable safety issue associated with chronic tolvaptan use, newly identified in Trial 156-04-251, is the potential for idiosyncratic hepatic toxicity. With a once every 4 month monitoring scheme, an imbalance in the proportion of subjects with elevated transaminases (tolvaptan > placebo) led to identification of 3 subjects (total from both Trial 156-04-251 and its open-label extension trial, 156-08-271) with laboratory and clinical evidence of potentially serious drug-induced liver injury (DILI). Based on the available data from the aforementioned trials, the sponsor proposed that appropriate subject monitoring and management be implemented to mitigate this potential risk in the ADPKD population. For this trial, standard liver parameters will be measured at baseline and then monthly thereafter.

Significant events related to glaucoma and skin neoplasms were also observed; however the causal relationship to tolvaptan remains uncertain. These adverse events (AEs) and the above attributable adverse reactions should be considered in light of the benefits of a reduced risk of ADPKD kidney complications, including renal pain, urinary tract infection, hematuria, anemia, and nephrolithiasis.¹⁰

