3.1 Type/Design of Trial

The trial will comprise 2 phases as described below:

Phase A is a randomized, double-blind, placebo-controlled phase to compare tolvaptan with placebo. The duration of treatment is 12 months. It is open to subjects between the ages of 4 and 17 years, inclusive. Subjects between the ages of 12 and 17 years will be stratified by age and gender as described in [Section 3.3](#). When these stratified cohorts have been closed, enrollment for the trial will end ([Figure 3.1-1](#)). Additionally, subjects aged 4 to 11 years may be eligible for participation following discussion with the medical monitor.

Qualified subjects who complete Phase A may continue into Phase B. A qualified subject is defined as one who is willing to continue in the trial and who does not have any AEs that would require IMP discontinuation.

Phase B is an open-label phase during which subjects who have completed Phase A of the trial will receive treatment with tolvaptan for 24 months ([Figure 3.1-2](#)). The purpose of Phase B is to obtain safety and efficacy data for long term use of tolvaptan.

When all subjects in Phase A have either completed the Month 12 visit or early terminated from the trial, a snapshot of the data will be taken. At that time, the snapshot will be unblinded, and results analyzed and reported in an interim clinical study report (CSR) to provide early information on safety. The protocol may be amended to further ensure continuing safety and tolerability measures are in place (Refer to [Section 13](#) for the Amendment policy).

Protocol 156-12-298

When all subjects in Phase B either complete the Month 24 visit, or the last ongoing subject terminates early, the database will be locked, and a final CSR will be provided to the regulatory authorities.

[figure not shown]

Figure 3.1-1 Trial Design Schematic Phase A, Randomized, Double-blind

^aSubjects between the ages of 4 and 11 are eligible for the trial but are not included in the age cohorts.

[figure not shown]

Figure 3.1-2 Trial Design Schematic Phase B, Open-Label

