5.7 Follow-up of Adverse Events

For this trial, information on AEs will be collected from the signature of the informed consent until 14 days after the last dose of IMP has been administered or until 7 days in subjects who discontinued prior to randomization. Follow-up of AEs is described below.

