3.2.2 Treatment in Phase B

Subjects who have completed Phase A on treatment and continue in Phase B will receive open-label tolvaptan for up to 24 months. In order to preserve the blind in Phase A, subjects will be started at a dose based on their current body weight (see [Table 3.2.1-1](#)) and after 1 week, they will be asked to up-titrate once from their starting dose. Subjects who wish to lower their dose secondary to tolerance will have their doses adjusted as necessary.

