9.1 Extent of Exposure

A subject's duration of exposure is defined as the trial medication end date - trial medication start date + 1 in each phase. Duration of exposure will be summarized by

Protocol 156-12-298

treatment group in Phase A and by previous Phase A treatment group (Tolvaptan and placebo) and pooled in Phase B.

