9.2 Adverse Events

All adverse events (AE) will be coded by MedDRA System Organ Class (SOC) and Preferred Term (PT). A treatment-emergent AE (TEAE) is defined as an AE which starts after start of trial medication), or an AE continues from baseline of the specific phase and becomes serious, worsening, trial drug-related or results in death, discontinuation, interruption or reduction of trial medication during this phase. The incidences of the following treatment-emergent adverse events (TEAEs) will be summarized by treatment groups:

- TEAEs by severity
- Potentially drug-related TEAEs
- TEAEs with an outcome of death
- Serious TEAEs
- Discontinuations due to TEAEs

Incidences of AEs above will be tabulated by treatment for Phase A safety dataset and Phase B safety dataset, respectively.

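### TEAEs are summarised only as crude incidence within each phase, with no time-at-risk denominator, so unequal observation time can distort comparisons of later-onset events

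*SAP*

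**What the plan says.** SAP 9.2 lists the TEAE summaries and states: "Incidences of AEs above will be tabulated by treatment for Phase A safety dataset and Phase B safety dataset, respectively". Protocol 7.9.1 likewise summarises incidence by treatment group. In the readable text of both documents, no AE table has a person-time denominator, and no cumulative-incidence or interval summary of AEs is planned.

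The surrounding provisions are:

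- **Phase length.** Protocol 3.1 says of Phase A: "The duration of treatment is 12 months". In Phase B, subjects "will receive treatment with tolvaptan for 24 months". SAP 3.2.2 words this as "will receive open-label tolvaptan for up to 24 months".
- **AE collection.** Protocol 5.7 collects AEs "until 14 days after the last dose of IMP has been administered".
- **TEAE definition.** SAP 9.2: "A treatment-emergent AE (TEAE) is defined as an AE which starts after start of trial medication". It also covers events continuing from baseline that worsen. It gives no end date after the last dose.
- **Exposure.** SAP 9.1: "Duration of exposure will be summarized by" treatment group in Phase A, and by previous Phase A group and pooled in Phase B. It is not linked to the AE tables.
- **Aquaretic events.** SAP 8.3 and SAP 9 name a rate of aquaretic AEs but define no denominator.
- **Reporting.** SAP 6 reports the two phases separately.

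**The concern.** A crude proportion is a fair summary when everyone is observed for about the same time. Here there are two reasons why they may not be.

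First, AE collection is tied to the last dose, so a subject who stops early is observed for less time. Protocol 1.3 says that the aquaretic reactions seen in adults occur early and "are most likely to limit a subject's ability to continue therapy". If that carries over to this trial, tolvaptan subjects would have less time in which a later-onset event could be recorded.

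Second, Phase B is twice as long as Phase A. The same underlying rate therefore gives a larger proportion in the Phase B table with no change in risk.

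At stake is the primary objective, long-term safety. The analysis is descriptive, so no later modelling step would correct a proportion distorted by observation time.

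**Working it through.** The documents give no AE rate, no stopping rate and no power calculation, so there is no planned figure to reproduce. The inputs taken from the documents are T = 1 year for Phase A, 2 years for Phase B, and a collection window of 14 days. Event rates and stopping fractions are assumptions, shown over a range. The event hazard h is constant throughout.

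**1. Early stopping on tolvaptan only, at 1 month.** With a fraction s stopping:

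incidence = (1 − s)(1 − e^(−h)) + s(1 − e^(−h(1/12 + 14/365.25)))

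With h = 0.3, full observation gives 1 − e^(−0.3) = 25.9%. A stopper is observed for 0.0833 + 0.0383 = 0.1217 years, giving 1 − e^(−0.0365) = 3.6%.

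| Stopping on tolvaptan | Calculation | Tolvaptan | Placebo |
|---|---|---|---|
| 10% | 0.9 × 25.9 + 0.1 × 3.6 | 23.7% | 25.9% |
| 20% | 0.8 × 25.9 + 0.2 × 3.6 | 21.5% | 25.9% |
| 30% | 0.7 × 25.9 + 0.3 × 3.6 | 19.2% | 25.9% |

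The true rate is the same in both arms. At 20% stopping the crude ratio is 21.5/25.9 = 0.83.

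**2. Gradual stopping.** Let the stopping time U be exponential with hazard −ln(1 − s), with 5% stopping per year on placebo. Events count to min(U + 14 days, 12 months), and incidence is the average of 1 − e^(−h × observed time). The placebo 12-month risk is 20%, so h = −ln(0.8).

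| Stopping on tolvaptan | Crude ratio, true hazard ratio 1.0 | Crude ratio, true hazard ratio 1.5 | Risk difference, true hazard ratio 1.5 |
|---|---|---|---|
| 5% (equal) | 1.00 | 1.42 | 8.3 points |
| 10% | 0.98 | 1.39 | 7.6 points |
| 20% | 0.93 | 1.32 | 6.3 points |
| 30% | 0.88 | 1.25 | 4.9 points |
| 40% | 0.82 | 1.18 | 3.5 points |

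With full observation, a hazard ratio of 1.5 gives a risk ratio of 1.42 and a difference of 8.45 points. The loss in risk difference runs from about 10% (10% stopping) to about 59% (40% stopping). With equal stopping the ratio is essentially unbiased.

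**3. Early events.** At 20% stopping per year, 1 − 0.8^(28/365) = 1.7% have stopped by day 28. Events that arise in the first weeks are barely affected.

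**4. Phase length.** With h = 0.3 and no stopping, 12 months gives 1 − e^(−0.3) = 25.9% and 24 months gives 1 − e^(−0.6) = 45.1%. More generally, a 12-month risk p becomes 1 − (1 − p)² over 24 months. Risks of 10%, 20% and 30% become 19%, 36% and 51%, which are ratios of 1.9, 1.8 and 1.7 at an unchanged hazard. With 10% to 30% stopping per year, the ratio runs from 1.81 to 1.49 over these risks.

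**5. Does a rate repair this?** Time at risk to first event is incidence/h when the hazard is constant. In the 20% row of step 1 that is 0.2145/0.3 = 0.715 years per tolvaptan subject, against 0.2592/0.3 = 0.864 on placebo. First events per 100 subject-years are then 30.0 in both arms, as they should be.

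**The case against.** The strongest reply is that the imbalance in Phase A may not exist. No stopping rate by arm is given anywhere. The remark in protocol 1.3 concerns adults, and the plan works against early stopping: protocol 2.2 adjusts starting doses for body weight and protocol 3.2.1 allows down-titration. All of that stands, so more stopping on tolvaptan is an assumption.

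A reader might also infer that AE observation ends with the drug. The documents do not support that. Collection runs 14 days past the last dose, discontinuers are followed every 6 months through the phase (protocol Table 3.7-1 footnote c and 3.8.3.2), and protocol 5.7.1 has nonserious AEs recorded whenever they are identified during the trial. With no end date in the TEAE definition, AEs found at off-drug visits might count. If they do, much of the Phase A imbalance disappears. The text leaves this unresolved, which is a reason to define time at risk.

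It can be added that no between-phase comparison is planned, and that exposure, reasons for discontinuation and TEAE discontinuations are all tabulated, so unequal stopping would be visible. That is fair. But mean exposure includes time after a first event, so it does not give time at risk to first event. Phase B also has no concurrent control, which invites readers to set its table against Phase A.

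Finally, the trial is small. With about 50 subjects per arm (about 100 in total, 1:1), the standard error of one proportion of 25.9% is √(0.259 × 0.741/50) = 6.2 points, so the shift in step 1 is comparable to sampling error. This limits what any single table shows. It does not remove a shift that would run in the same direction across all later-onset events.

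**Conclusion.** The concern holds in limited form. The only defined TEAE measure is crude incidence within each phase.

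If tolvaptan subjects stop earlier, the Phase A comparison of later-onset events is shifted towards tolvaptan: by 2.2 to 6.7 points under the sharp pattern in step 1, and by less with gradual stopping at the same fraction. It is about nil with equal stopping and negligible for aquaretic events in the first weeks. These sizes rest on a constant hazard, the assumed stopping fractions, and AE counting that ends 14 days after the last dose.

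A reader might infer that crude incidence hides an excess risk on tolvaptan. That is too strong. Under gradual stopping, a true hazard ratio of 1.5 still shows as a crude ratio of 1.39 to 1.18 across 10% to 40% stopping, so the excess is attenuated but remains visible.

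The phase-length effect needs no assumption about differential stopping: 25.9% against 45.1% at the same rate of 0.3 per year. A reader might infer that rates would make the phases comparable. They would not, because Phase B is uncontrolled and admits only subjects who completed Phase A on treatment (protocol Table 3.7-1 footnote c).

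**What to change.** In SAP 9.2:

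- Add to each TEAE table, next to n (%), the number of subjects with a first event per 100 subject-years at risk. Time at risk runs from the first dose in the phase to the earliest of first event, end of the AE collection window, or phase end. Show it by arm in Phase A, and by previous Phase A arm and pooled in Phase B.
- Give the TEAE definition an end date that agrees with protocol 5.7, so that counted events and time at risk cover the same period.
- Use the same denominator for the rate of aquaretic AEs in SAP 8.3 and SAP 9.
- Keep n (%) as the headline for early-onset events.
- State that the rates remove only the phase-length artefact and do not make Phase A and Phase B directly comparable, for the reasons given above.

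The cost is one extra column per table, from dates already collected, with no change to trial procedures. The downside is that a single rate assumes a roughly constant hazard, which is why n (%) stays in every table and leads for events that cluster in the first weeks.

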9.3 Clinical Laboratory Data

Summary statistics for changes from baseline in the clinical laboratory measurements will be provided for the safety population. Potentially clinically significant results in laboratory tests identified using prospectively defined criteria will also be summarized.

According to the Food and Drug Administration (FDA) Guidance², laboratory measurements that signal the potential for drug-induced liver injury (DILI) will be reported. An incidence table and a listing will be provided for subjects who meet one or combinations of the following criteria:

- 1) ALT (alanine transaminase) or AST (aspartate transaminase) $\geq 3x$ upper limit of normal (ULN) (or baseline value for subjects with abnormal baseline)
- 2) Increase in bilirubin $\geq 2x$ ULN (or baseline value for subjects with abnormal baseline)

Protocol 156-12-298

9.4 Vital Sign Data

Summary statistics for changes from baseline in vital signs and potentially clinically significant results in vital signs will be summarized for the safety population. For a subject with repeat measures in either vital signs or lab tests at a visit, the last repeat will be used in the by visit summary. However, for outlier analysis (such as clinically significant abnormalities), data from all visits, no matter they are from the original visits, repeats, or unscheduled visits, will be included.

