4.1 Prohibited Medications

Medications or surgical therapies used for the purpose or potential for modifying the progression of PKD cyst growth or development will be prohibited. These include, but are not restricted to, somatostatin agonists, rapamune (sirolimus), anti-sense ribonucleic acid (RNA) therapies, tolvaptan, and other vasopressin antagonists eg, OPC-31260 (mozavaptan), Vaprisol (conivaptan), or agonists (eg, desmopressin). If a subject develops a medical need for cyst reduction therapy, during trial participation, this will be addressed with the appropriate physician. The subject would then be discontinued from treatment at the time of surgical intervention. The subject will remain in the trial and may restart treatment 6 weeks after surgical intervention at the discretion of the investigator.

Continuous or short-term use of other medications, while not prohibited, may be restricted by the investigator because of their potential for interference with metabolism or efficacy endpoints. This includes the use of diuretics which may be used intermittently, but not within 7 days of a urine assessment. Diuretics are not generally recommended in ADPKD due to their tendency to increase AVP levels through relative dehydration or volume depletion; thus, chronic use of diuretics (eg, for hypertension) will be prohibited due to potential endpoint interference and is an exclusionary criterion for this trial. Subjects taking such agents must first sign an ICF and then agree to be switched to an alternate form of therapy in order to be eligible for the trial. Subjects must be on a stable dose of their antihypertensive medications at randomization.

Some drugs are known to alter creatinine concentrations so, while not prohibited, subjects should alert their trial doctor, and any other healthcare providers, to take this into consideration when considering changes in their prescribed or over-the-counter

Protocol 156-12-298

medications. A brief list would include: cimetidine, nonsteroidal antiinflammatory drug medications like aspirin or ibuprofen, chemotherapy drugs, and cephalosporin.

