5.4.2.3 Subjects with Elevated Liver Transaminase at Screening

Subjects found to have liver laboratory abnormalities at screening or who have a history of non-ADPKD-related liver disease will require further evaluation. These subjects will need to have the special liver eCRF (see [Section 5.4.5](#)) completed and additional testing

Protocol 156-12-298

will be required during screening to confirm the stability of the abnormality prior to randomization to confirm eligibility. Management of such subjects should be closely coordinated with the trial's medical monitor. In these subjects, further changes in liver test levels of $> 2 \times$ upper limit of their highest screening value at any point postscreening should prompt re-testing within 48 to 72 hours. Should such an increase occur during treatment with IMP, the subject will be immediately discontinued from treatment. IMP should not be resumed until monitoring indicates abnormalities have resolved, are stable or are not rapidly increasing, and then only with an increased frequency of monitoring.

Protocol 156-12-298

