9.6 Electrocardiogram Data

Electrocardiogram (ECG) data will not be summarized since ECG data will be collected at the screening visit only.

10 Pharmacodynamic Analyses

Urinary excretions will be determined as urine concentration \times urine volume; missing values will not be imputed. If urine concentration or volume is missing for any interval, the 0 to 24 hour values will not be determined. Urine volumes of zero, and consequently non reportable urine concentration, are not considered as missing data; values of 0 will be reported for volume and excretion.

Free water clearance will be determined as urine excretion rate – osmolar clearance.

Osmolar, sodium, and creatinine clearances will be determined by standard methods with average serum concentration determined by averaging the concentrations at the beginning and end of the urine collection interval. If urine volume for a collection interval is 0, then the clearance value for that interval and the following interval will be determined by using the average value of the 3 serum concentrations, the urine volume of the second interval and the total time of the 2 collection intervals (eg, 2 to 4 hour collection has urine volume of 0 mL). Clearance for the 2 to 4 and 4 to 8 hour intervals will be determined using serum concentrations at 2, 4, and 8 hours, the urine volume from 4 to 8 hour interval and total collection time of 6 hours (8 minus 2).

Values of urine osmolality will be summarized with descriptive statistics by total daily dose (all placebos grouped together) and collection interval. Sodium and creatinine urine concentrations will only be listed.

Protocol 156-12-298

Values of excretions (osmoles, sodium, and creatinine) and clearances (free water, sodium, and creatinine) will be summarized with descriptive statistics by total daily dose (all placebos grouped together), collection interval, and 0 to 24 hours.

Serum concentrations (osmolality, sodium, and creatinine) and change from predose will be summarized with descriptive statistics by total daily dose (all placebos grouped together), analyte, and time point.

11 Interim Analysis

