Appendix 2: Criteria of Potentially Clinically Significant Vital Sign Abnormalities

[figure not shown]
Test Parameters	Unit	Age	Criteria (meet either one will count)	
			Limit	Change from baseline
Heart Rate	bpm	4 - 14 Years	<= 50 >= 140	Decrease >= 15 Increase >= 15
		15 Years and older	<=50 >= 120	Decrease >= 15 Increase >= 15
SBP, Sitting	mmHg	4 – 12 Years	<=70 >= 130	Decrease >= 20 Increase>=20
		13 – 17 Years	<= 120 >= 144	Decrease >= 20 Increase>=20
DBP, Sitting	mmHg	4 – 12 Years	<= 50 >= 86	Decrease >= 15 Increase>=15
		13 – 17 Years	<= 80 >= 92	Decrease >= 15 Increase>=15

Protocol 156-12-298

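### The counts of potentially clinically significant results have no post-dose window and mostly no baseline condition, so stable pre-existing abnormalities are counted

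*SAP*

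**What the plan says.** SAP 9.4 first settles repeat values for the summaries by visit: "For a subject with repeat measures in either vital signs or lab tests at a visit, the last repeat will be used in the by" [...]. It then sets a different rule for outliers and defines the records used: "for outlier analysis (such as clinically significant abnormalities), data from all visits, no matter they are from the original visits, repeats, or unscheduled visits". The first sentence names both vital signs and laboratory tests, so the rule is taken to cover both.

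The criteria are in the appendices. Appendix 2 (vital signs) has one column of absolute limits and one of changes from baseline, under the heading "Criteria (meet either one will count"). Appendix 1 (laboratory) grades each test against fixed values or multiples of the normal limit, except creatinine, which is graded as a multiple of baseline. SAP 9.3 adds only this: "Potentially clinically significant results in laboratory tests identified using prospectively defined criteria will also be summarized".

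SAP 9 defines a safety baseline for each phase: the last value before randomization for Phase A, and the last value before the first Phase B dose for Phase B. No sentence uses either one to restrict the PCS counts, and Protocol 7.9.2 and 7.9.3 add no restriction. Adverse events are handled differently. SAP 9.2 says "A treatment-emergent AE (TEAE) is defined as an AE which starts after start of trial medication", and adds a worsening rule for events already present. Laboratory tests and vital signs have no counterpart, and no shift table is planned.

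**The concern.** There are two gaps, and the second does not depend on the first.

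- **No window.** SAP 9.6 itself treats screening as a visit ("ECG data will be collected at the screening visit only"). Protocol Table 3.7-1 takes laboratory tests and vital signs at screening, and vital signs again on Day 1. Taken literally, the rule reaches values obtained before any drug. The Phase A Month 12 visit is also the Phase B baseline, so one value could be counted in both phases.
- **No baseline condition.** If programmers drop pre-dose values, a child whose value was outside the limit at entry and stays there is still counted at the first post-dose visit.

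The protocol allows some abnormal entrants. ALT or AST above ULN but below 1.5 × ULN is eligible and is Grade 1 in Appendix 1. Protocol 5.4.2.3 provides for "Subjects found to have liver laboratory abnormalities at screening". Protocol 4.1 says "Subjects must be on a stable dose of their antihypertensive medications at randomization", so treated hypertensive children may enter.

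The primary objective is long-term safety. In Phase A, subjects abnormal before treatment add the same expected count to both arms and pull the contrast toward the null. In Phase B, which has no control arm, their abnormalities appear under tolvaptan.

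**Working it through.** **Inputs from the documents.** Allocation is 1:1 (Protocol 3.6). At least 60 subjects aged 12 to 17 are planned (Protocol 7.1, SAP 4), so 60/2 = 30 per arm. Neither document gives a PCS rate, a baseline prevalence or a power figure, so there is no planned figure to reproduce.

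**Assumptions.** b is the share of each arm that already meets a criterion at baseline, equal in expectation by randomization. pC and pT are the new-onset risks on placebo and tolvaptan among subjects who do not meet it.

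**Step 1: Phase A, pre-dose values counted.** The proportion shown in an arm is b + (1 − b)p. The difference shown is (1 − b)(pT − pC). With pC = 10%, pT = 30% and b = 10%, placebo shows 0.10 + 0.90 × 0.10 = 19% and tolvaptan shows 0.10 + 0.90 × 0.30 = 37%.

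| b | Placebo | Tolvaptan | Difference (points) | Ratio |
|---|---|---|---|---|
| 0% | 10% | 30% | 20 | 3.00 |
| 5% | 14.5% | 33.5% | 19 | 2.31 |
| 10% | 19% | 37% | 18 | 1.95 |
| 20% | 28% | 44% | 16 | 1.57 |
| 30% | 37% | 51% | 14 | 1.38 |
| 50% | 55% | 65% | 10 | 1.18 |

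With assumed risks of 5% and 20% instead, the ratio of 4.00 becomes 1.93 at b = 10% and 1.31 at b = 30%.

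**Step 2: Phase A, post-dose values only.** Let a share s of the baseline-abnormal subjects stay abnormal at one or more post-dose visits. The proportion shown is bs + (1 − b)p. If s is the same in both arms, the difference is again (1 − b)(pT − pC). A window alone therefore does not restore the contrast.

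**Step 3: chance imbalance.** With 30 per arm, the difference between arms in baseline prevalence has standard deviation √(2b(1 − b)/30). This is 7.7 points at b = 10% and 12.9 points at b = 50%. Dilution is an expectation. In one trial of this size the imbalance can push the contrast either way.

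**Step 4: Phase B.** The excess over the new-onset risk is b + (1 − b)p − p = b(1 − p). With p = 30%, it is 0.10 × 0.70 = 7 points at b = 10% and 0.30 × 0.70 = 21 points at b = 30%.

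**Step 5: the denominator.** Suppose new abnormalities are counted but all subjects stay in the denominator. At b = 10% the table shows 0.90 × 10% = 9% against 0.90 × 30% = 27%. The ratio of 3.00 is recovered, but the difference stays at 18 points. With only the subjects who did not meet the criterion at baseline in the denominator, the table shows 10% against 30%.

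**Step 6: which criteria are exposed.** Exposed: the Appendix 2 limits and all Appendix 1 grades except creatinine. Largely unaffected: the creatinine grades, the change-from-baseline column of Appendix 2, and the liver-injury criteria in SAP 9.3 for subjects with an abnormal baseline, where the baseline value replaces ULN.

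**The case against.** **The sentence may only settle which records are kept.** It follows directly on the rule for repeats, and its list (original, repeat, unscheduled) concerns duplicates. A reader might infer that the SAP prescribes counting screening values as on-treatment events. The documents do not say so. They only fail to exclude it. This answers the missing window in part, but it does not touch the missing baseline condition.

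**Other safety outputs are planned.** A reader might take the PCS tables as the main laboratory and vital-sign output. SAP 9.3 and 9.4 also plan change-from-baseline summaries, the listed safety endpoint is worded as changes from baseline, and adverse events carry a treatment-emergent rule. This stands and limits the weight of the point.

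**The hepatic signal is mostly protected.** Eligible ALT and AST elevations are at most Grade 1, and Grade 2 starts above 3 × ULN. Appendix 1 does not say that Grade 1 alone counts as PCS. If results are shown by grade, a child who goes from Grade 1 to Grade 3 appears at Grade 3. The formula then applies grade by grade, with b close to zero at the higher transaminase grades. This stands.

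**The evidence on abnormal entrants is thin.** A child on stable antihypertensive treatment need not exceed a limit, and Protocol 5.4.2.3 calls for extra testing to confirm eligibility. Appendix 2 as printed lists systolic pressure at or below 120 and diastolic pressure at or below 80 mmHg as limits for ages 13 to 17, which would make b large for those criteria. Whether those limits are as intended is a separate question, and the present point does not rest on them.

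**Conclusion.** The gap is real and should be closed. No section of either document gives the PCS counts a post-first-dose window, and most criteria have no baseline condition. Followed as written, the plan counts stable pre-existing abnormalities.

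The direction in Phase A is an expected shrinkage of the risk difference by the factor (1 − b). In Phase B the direction is inflation. The size is unknown, because b and the new-onset risks used above are all assumptions. At b = 10% the assumed difference loses only 2 of 20 points, although the ratio falls from 3.00 to 1.95. The trial is descriptive, so the cost is in how the tables read and not in a formal test. The documents do not show that a tolvaptan signal would be hidden, nor that the long-term safety objective depends on these tables alone.

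**What to change.** In SAP 9.4, for both laboratory tests and vital signs:

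- Restrict PCS counts to values after the first dose of IMP in the phase, whether scheduled, repeat or unscheduled.
- Count a subject under Appendix 1 only if the worst post-dose grade exceeds the baseline grade.
- Count a subject under an Appendix 2 limit only if the baseline value did not meet that limit, and use as denominator the subjects whose baseline did not meet it (Step 5).
- Add a shift table from baseline grade to worst post-dose grade.
- In Phase B, use the Phase B baseline that SAP 9 already defines, and present results by previous Phase A treatment group, as SAP 8.3 and 9.1 do for other outputs. For subjects previously on tolvaptan, also show worsening against the Phase A pre-dose baseline, so that an abnormality that arose on tolvaptan in Phase A is not hidden.

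The Phase A baseline should not be the sole Phase B reference for every subject. An abnormality that arose on placebo and persisted would then count as new under open-label tolvaptan.

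The cost is a short SAP revision, the shift table and one extra Phase B display for previous tolvaptan subjects, all from data already collected. The counts will be smaller than under the present rule.
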